4.4.3. Reasons and details of presented data

We expect to have no lost-to-follow up, because all study participants are dialysis patients actively on dialysis. The amount of patients and their different reasons for withdrawal will be presented in a flow chart.

4.5. Interim Analysis population

All patients who were enrolled and randomized in the trial at the time of the interim analysis.

4.6. Final analysis population

All patients who were enrolled and randomized in the trial.

4.7. Baseline patient characteristics

Baseline characteristics will include age (years, continuous), gender (men/women), dialysis details (vascular access (fistula/graft), sessions per week, duration of treatment in hours, baseline access flow in mL/min), medical and vascular access history, smoking history, use of anticoagulants.

4.8. Details of how baseline characteristics will be descriptively summarized

Baseline characteristics will be presented in a table by treatment arm after the initial randomization. Means and standard deviations (SDs) will be used to report continuous variables, and median and interquartile ranges (IQR) to report categorical values. (See tables and figures – Section 1)

5. Analysis

5.1. Outcome definitions

5.1.1. Primary outcome

The primary outcome will be defined as the number of interventions required for each patient-year of hemodialysis treatment (number of interventions per patient-year). This core outcome measure was defined in an international consensus workshop including patients, clinicians, researchers, policy makers and industry representatives, and includes all percutaneous access interventions (including central venous catheter placement, removal and guidewire exchange, angioplasty, stent placement, percutaneous thrombectomy) and surgical access procedures (including subsequent access placements if the current access failed, and surgical revisions to promote maturation or maintain long-term patency, including open thrombectomy). Interventions that are done under general anesthesia or that require hospital admission of more than one day are scored as major interventions, whereas interventions under local or locoregional anesthesia as day-case of office procedures are scored as minor interventions. These interventions correspond to grade 3A and 3B surgical complications in the Clavien-Dindo classification (30). Access-related complications that are resolved using conservative or pharmacological treatment are not considered as interventions.

5.1.2. Secondary outcomes

1. Access-related complications per patient-year

Separate analyses will be performed on access-related complications graded as Clavien-Dindo grade 2 or higher and on access-related complications graded as Clavien-Dindo grade 4 or 5. The outcome will be defined as the number of access-related complications per patient-year.

- Access-related complications of Clavien-Dindo grade 2 or higher will be registered (30). Grade 2 complications require pharmacological treatment including catheter thrombolysis, antibiotics and blood transfusions. Complications that require no pharmaceutical or interventional treatment (grade 1) are not considered relevant for this clinical trial.
- Access-related complication of Clavien-Dindo grade 4 or 5 (i.e. admission to intensive care unit or death) are considered serious adverse events. As an exception, postoperative intensive care unit admission for vasopressor therapy to prevent early vascular access thrombosis is not considered a serious adverse event or complication.

2. Vascular access thrombosis rate

Vascular access thromboses will be defined as the absence of thrill and bruit, with confirmation of no flow by duplex ultrasound if deemed necessary by the treating physician at the study site. The outcome will be defined as the number of vascular access thrombosis events per person-year.

3. All-cause mortality

All-cause mortality will be defined as death by any cause during follow-up.

4. Access-related health care costs from randomization until the end of follow-up

Healthcare costs will be derived from hospital registration systems at the individual participant level. Costs to patients and families will be measured at the individual participants level using a study-specific adaptation of the Medical Consumption Questionnaire and Productivity Cost Questionnaire

developed by the institute for Medical Technology Assessment. Patients will be asked to report the data from their cost questionnaire every 3 months during the follow-up period.

5. Patient-reported outcome measures

For the patient-reported outcome measures the Short-form Vascular Access Questionnaire (SF-VAQ) and the Dutch version of the 5-level EuroQol 5-dimensional questionnaire (EQ-5D-5L) will be used.

- SF-VAQ measured at baseline and every 3 months during the follow-up period. The Short-Form Vascular Access Questionnaire (SF-VAQ) was developed to measure hemodialysis patients' satisfaction with their vascular access (31). The questionnaire contains 13 items (7-point Likert scale) in 4 domains (overall satisfaction, physical symptoms, social functioning and complications), and has a single summary score.

- EQ-5D-5L measured at baseline and every 3 months during the follow-up period. The EQ-5D-5L was developed to measure health-state utility values. The questionnaire contains self-classifiers at 5 levels in 5 dimensions (mobility, self-care, usual activities, pain/discomfort and anxiety/depression) (32). Utility values will be calculated from these health states using preferences elicited from the Dutch general population (36). Quality-adjusted life years will be calculated with these utility values using the area under the curve method.

6. Quality of the surveillance program

- Repeatability and reproducibility of vascular access flow volume measurements (mL/min) using ultrasound dilution in routine clinical practice.
- Diagnostic accuracy of vascular access flow volume measurements to predict clinical signs of flow dysfunction and access thrombosis within 1 month in the intervention group. Diagnostic accuracy will be reported as sensitivity, specificity, negative predictive value, and positive predictive value.
- The percentage of vascular access balloon angioplasties that have resulted in technical success (residual stenosis <30%) and clinical success (increase in flow volume to >500mL/min, restoration of vascular access function and resolution of any clinical signs of flow dysfunction).
- Vascular access primary, primary assisted, and secondary patency after balloon angioplasty (time to event).
- Adherence (in %) to the vascular access follow-up protocol and to the study protocol for referral to correct vascular access stenosis.

7. Other outcome measures will be registered for explanatory analyses and are defined according to the ESVS guidelines on vascular access (1):

- Primary patency of vascular access (intervention-free vascular access survival): the interval (in days) between randomization and the first intervention for vascular access dysfunction or thrombosis or its abandonment.
- Assisted primary patency of vascular access (thrombosis-free vascular access survival): the interval (in days) between randomization and the first occlusion or its abandonment.
- Secondary patency of vascular access: the interval (in days) between randomization and the day on which the vascular access is deemed to be permanently unusable (i.e. access abandonment).
- The number of hemodialysis sessions with cannulation difficulties (i.e. needing >1 attempt to place and secure two dialysis needles) and cannulation failure (i.e. the inability to place and secure two dialysis needles) per patient-year of hemodialysis treatment.
- Days in hospital per patient-year for any reason and for vascular access-related reasons.

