Monitoring reports ^a person-years person-years
Flow measurements person-years person-years

Table 2G: Vascular access dysfunction detected by monitoring and surveillance - Monitoring reports

	Monitoring (... reports)	Surveillance (... reports)	P
Clinical indicators of flow dysfunction	%	%	...
Physical examination	%	%	...
Weak or discontinuous thrill	%	%	...
High pitched or discontinuous bruit	%	%	...
Hyperpulsatile vascular access	%	%	...
Weak vascular access	%	%	...
No thrill or bruit	%	%	...
Recurrent problems during dialysis	%	%	...
Inability to achieve target blood flow	%	%	...
New cannulation problems	%	%	...
Prolonged bleeding	%	%	...
Unexplained fall in dialysis efficiency	%	%	...
Other findings at inspection			
Aneurysm	%	%	...
Hand ischemia	%	%	...
Infection	%	%	...
Edema	%	%	...
Skin lesions	%	%	...
Hematoma	%	%	...

Statistical analysis: Chi squared tests.

Table 2H: Vascular access dysfunction detected by monitoring and surveillance - Surveillance flow measurements

	Monitoring (... measurements)	Surveillance (... measurements)	P
Access flow <500 mL/min ^b	%	%	...
With clinical indicators of flow dysfunction	%	%	...
Without clinical indicators of flow dysfunction	%	%	...
Access flow 500-1000 mL/min with >20% reduction from baseline ^c	%	%	...
With clinical indicators of flow dysfunction ^d	%	%	...
Without clinical indicators of flow dysfunction ^d	%	%	...

Data are presented as proportions. The sum of the proportions may not add up to 100% because patients may have more than one clinical indicator of flow dysfunction.

^a Monitoring reports were not transferred to the research database in two study sites (OLVG and MUMC+ from 11-2024 onwards) because of technical issues with the electronic patient files.

^b Access flow is considered <500 mL/min only when the initial low flow measurement was confirmed in a subsequent dialysis session.

^c Baseline is the first flow measurement after randomization.

[figure not shown]
^d Clinical indicators of flow dysfunction refer to the decision rules for interventions defined in the study protocol (used to send notifications to the study sites).

When counting flow measurements, only measurements for surveillance and confirmatory measurements after low flow are counted. Flow measurements to evaluate interventions or as random repeats are excluded from analysis.

[figure not shown]
Statistical analysis: Chi squared tests.

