Statistical analysis (intention to treat population): general linear mixed effect model with Poisson distribution and identity link, and with time as off-set variable. The outcome will be expressed as a ratio (exponential of β_1) of events (number of interventions) per 1 unit increase of exposure time between both groups. A random intercept for each individual participant will be estimated to account for dependence of observations. Expected counts will be plotted against observed counts to check whether the distribution of counts follow a Poisson distribution. Furthermore, the Pearson dispersion statistic will be assessed to check whether there is equidispersion of the variance compared to the mean. In case of overdispersion of the data, a quasi-Poisson model or negative binomial model will be performed.

Stratification: study site and vascular access type (fistula / graft).

Subgroup analysis: vascular access type (fistula / graft).

Sensitivity analysis:

- Major interventions counting twice (see Table 3a-2)
- Exclusion of patients with interventions with technical failure (see Table 7A)
- Exclusion of patients with interventions with clinical failure (see Table 7A)

Table 3B: Characteristics of vascular access interventions

	Monitoring (N=...)	Surveillance (N=...)	P
Indication			
Clinical indicators of flow dysfunction ^a	%	%	...
Physical examination			
Weak or discontinuous thrill	%	%	...
High pitched or discontinuous bruit	%	%	...
Hyperpulsatile vascular access	%	%	...
Weak vascular access	%	%	...
No thrill or bruit	%	%	...
Recurrent problems during dialysis			
Inability to achieve target blood flow	%	%	...
New cannulation problems	%	%	...
Prolonged bleeding	%	%	...
Unexplained fall in dialysis efficiency	%	%	...
Access flow <500 mL/min without clinical indicators of flow dysfunction ^a	%	%	...
Vascular access thrombosis	%	%	...
New vascular access	%	%	...
Non-maturation	%	%	...
Central venous catheter dysfunction	%	%	...
Unused vascular access	%	%	...
Other than flow dysfunction	%	%	...
High flow	%	%	...
Central vein obstruction	%	%	...
Hand ischemia	%	%	...
Vascular access (pseudo)aneurysm	%	%	...
Vascular access infection	%	%	...
New vascular access	%	%	...
Non-maturation	%	%	...
Central venous catheter dysfunction	%	%	...
Unused vascular access	%	%	...
Anesthesia			...
Local anesthesia	%	%	
Local anesthesia with sedation	%	%	
Locoregional anesthesia	%	%	
Regional anesthesia	%	%	
Hospital admission			...
Outpatient	%	%	
Day case	%	%	

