
	N	Bias	Limits of agreement
Flow measurements within 2 weeks			
All measurements		mL/min	mL/min
Only random controls		mL/min	mL/min
Flow measurements within 1 week			
All measurements		mL/min	mL/min
Only random controls		mL/min	mL/min

Figure: Bland-Altman plots

- Y-axis: difference second – first measurement
- X-axis: mean second – first measurement
- Lines at bias and limits of agreement (95% CI)
- For each of the 4 subgroups in the table, with and without correction for blood pressure

Different observers under different conditions using the same measurement instrument (between session variation)

Include all ultrasound dilution flow measurements (with 3 replicates) repeated within 2 weeks

Check for assumptions of statistical model: normal distribution of measurements and homogeneity of variance within subjects

Table / Figure 6C: Agreement of ultrasound dilution and duplex flow measurements

Without correction for blood pressure

	N	Bias	Limits of agreement	ICC(2,1)
Flow measurements within 2 weeks		mL/min	mL/min	
Flow measurements within 1 week		mL/min	mL/min	

With correction for blood pressure

	N	Bias	Limits of agreement	ICC(2,1)
Flow measurements within 2 weeks		mL/min	mL/min	
Flow measurements within 1 week		mL/min	mL/min	

Figure: Bland-Altman plots

- Y-axis: difference ultrasound dilution – duplex measurement
- X-axis: mean ultrasound dilution – duplex measurement
- Lines at bias and limits of agreement (95% CI)
- For each of the 2 subgroups in the table, with and without correction for blood pressure

Different observers under different conditions using different measurement instruments (agreement)

Include all ultrasound dilution flow measurements (with 3 replicates) and duplex flow measurements for flow dysfunction done within 2 weeks

Check for assumptions of statistical model: normal distribution of measurements and homogeneity of variance within subjects

Table 6D: Diagnostic accuracy of vascular access surveillance to predict clinical indicators of flow dysfunction, thrombosis, and access loss

Cross-tables

	Intervention for clinical indicators of flow dysfunction <30 days		No intervention for clinical indicators of flow dysfunction <30 days		Total	
Access flow >500 mL/min	N	%	N	%	N	%
Access flow <500 mL/min	N	%	N	%	N	%
Total	N	%	N	%	N	100%
	Thrombosis <30 days		No thrombosis <30 days		Total	
Access flow >500 mL/min	N	%	N	%	N	%
Access flow <500 mL/min	N	%	N	%	N	%
Total	N	%	N	%	N	100%

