Clinical indicators of flow dysfunction refer to the decision rules for interventions defined in the study protocol (used to send notifications to the study sites).

The threshold for mean dynamic venous pressure will be derived from ROC curve analysis (Figure 10-2)

Calculate sensitivity, specificity, positive predictive value, and negative predictive value.

Figure 6E: Receiver operator characteristic (ROC) curves for diagnostic accuracy of absolute access flow to predict (A) interventions for clinical indicators of flow dysfunction <30 days, (B) thrombosis <30 days, and (C) loss of vascular access <30 days

Calculate area under the curve with 95% confidence intervals.

Figure 6F: Receiver operator characteristic (ROC) curves for diagnostic accuracy of relative access flow compared to baseline to predict (A) interventions for clinical indicators of flow dysfunction <30 days, (B) thrombosis <30 days, and (C) loss of vascular access <30 days

Calculate area under the curve with 95% confidence intervals.

Figure 6G: Receiver operator characteristic (ROC) curves for diagnostic accuracy of mean dynamic venous pressure to predict (A) interventions for clinical indicators of flow dysfunction <30 days, (B) thrombosis <30 days, and (C) loss of vascular access <30 days

Calculate area under the curve with 95% confidence intervals.

Figure 6H: Scatterplot of (A) absolute access flow to mean dynamic venous pressure, and (B) relative access flow compared to baseline to mean dynamic venous pressure

Statistical analysis: Pearson correlation coefficient with 95% confidence interval

Table 6I: Table / Figure 6B: Reproducibility / Inter-session reliability of vascular access monitoring

	Inter-session reliability (Cohen's kappa)
	Next dialysis session
Clinical indicators of flow dysfunction	...
Physical examination	...
Weak or discontinuous thrill	...
High pitched or discontinuous bruit	...
Hyperpulsatile vascular access	...
Weak vascular access	...
No thrill or bruit	...
Recurrent problems during dialysis	...
Inability to achieve target blood flow	...
New cannulation problems	...
Prolonged bleeding	...
Unexplained fall in dialysis efficiency	...
Other findings at inspection	...
Aneurysm	...
Hand ischemia	...
Infection	...
Edema	...
Skin lesions	...
Hematoma	...

The next dialysis session should be within 7 days of the initial assessment.

Table 6J: Diagnostic accuracy of vascular access monitoring to predict clinically relevant stenosis

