	Duplex ultrasound or intervention			No significant findings on multidisciplinary review of clinical indicators of flow dysfunction		
	N	Intervention <30 days (true positive)	No stenosis on imaging <30 days (false positive)	N	No intervention for clinical indicators of flow dysfunction, thrombosis, or loss of vascular access <30 days (true negative)	Intervention for clinical indicators of flow dysfunction, thrombosis, or loss of vascular access <30 days (false negative)
Clinical indicators of flow dysfunction	...	%	%	...	%	%
Physical examination	...	%	%	...	%	%
Weak or discontinuous thrill	...	%	%	...	%	%
High pitched or discontinuous bruit	...	%	%	...	%	%
Hyperpulsatile vascular access	...	%	%	...	%	%
Weak vascular access	...	%	%	...	%	%
No thrill or bruit	...	%	%	...	%	%
Recurrent problems during dialysis	...	%	%	...	%	%
Inability to achieve target blood flow	...	%	%	...	%	%
New cannulation problems	...	%	%	...	%	%
Prolonged bleeding	...	%	%	...	%	%
Unexplained fall in dialysis efficiency	...	%	%	...	%	%

Clinical indicators of flow dysfunction refer to the decision rules for interventions defined in the study protocol (used to send notifications to the study sites).

The sum of the counts may not add up to the total event rate because patients may have more than one clinical indicator of flow dysfunction.

Table 7A: Success rate of vascular access interventions for flow dysfunction

	All patients (N=...)		Monitoring (N=...)		Surveillance (N=...)		P
Technical success (<30% residual stenosis) ^a	%	N	%	N	%	N	...
Clinical success							
Access flow >500 mL/min	%	N	%	N	%	N	...
Resolution of clinical indicators of flow dysfunction ^b	%	N	%	N	%	N	...
Functional vascular access ^c	%	N	%	N	%	N	...

^a Only for percutaneous interventions

^b Only for interventions for clinical indicators of flow dysfunction

^c Functional vascular access is defined as: cannulated with 2 needles for 6 dialysis sessions in 30 days with prescribed dialysis blood flow

Statistical analysis: Chi squared tests

Figure 7B: Kaplan-Meier curves of (A) primary patency (any access-related intervention), (B)

assisted primary patency, and (C) secondary patency after interventions for flow dysfunction

Include interventions that result in functional vascular access. Censoring after loss of primary patency. Statistical comparison between monitoring and surveillance groups with log-rank tests.

Table 7C: Success rate of vascular access interventions for thrombosis

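### The sign that defines thrombosis is also counted as a clinical indicator of flow dysfunction, so an occluded access can score as a correct prediction of stenosis in Table 6J and fits two indications in Tables 3B, 8C and 8E

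*SAP*

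**What the plan says.** Section 5.1.2, item 2, defines the secondary outcome: "Vascular access thromboses will be defined as the absence of thrill and bruit". Duplex confirmation is left to the treating physician, so the examination finding alone can establish the event.

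The table shells use the same finding differently:

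- **Table 2G**, titled "Table 2G: Vascular access dysfunction detected by monitoring and surveillance - Monitoring reports", lists "No thrill or bruit" under physical examination, within the clinical indicators of flow dysfunction.
- **Table 3B** repeats that row among the clinical indicators that may be the indication for an intervention. It also has a separate indication row, "Vascular access thrombosis". Tables 8C and 8E likewise keep clinical indicators and thrombosis as distinct indication categories.
- **Table 6J**, titled "Table 6J: Diagnostic accuracy of vascular access monitoring to predict clinically relevant stenosis", has the same row among its index findings. A positive finding is scored under the column "Intervention <30 days (true positive" whenever an intervention follows. Among accesses cleared at multidisciplinary review, thrombosis within 30 days is one of the events that make a false negative.

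Footnotes to several of these tables say that the clinical indicators follow the protocol's decision rules, which are used to notify sites.

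**The concern.** A clinical indicator is meant to flag a stenosis while the access is still open. An access with neither thrill nor bruit has, by the SAP's own definition, already thrombosed. Placing that finding among the indicators mixes the warning with the event that the warning is meant to precede.

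Two things follow. First, Table 6J can credit clinical examination with predicting stenosis when it has only recorded an occlusion. Second, the indication for a thrombectomy is not determined: two analysts working from the same record could code it as flow dysfunction or as thrombosis. The split in Table 3B, and the indication variable in Tables 8C and 8E, would then depend on a choice made after the data are seen.

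**Working it through.** The SAP states no figure on this point, so there is none to reproduce. The check sets the definitions side by side.

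**Step 1: is it the same sign?** Section 5.1.2 requires thrill and bruit to be absent. The table row reads most naturally as neither being present, which is the same condition. If it were read as either one being absent, it would be wider but would still contain every thrombosis found at examination. The overlap holds on both readings.

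**Step 2: does a treated thrombosis meet the true-positive rule in Table 6J?** The column asks only for an intervention within 30 days. Section 5.1.1 counts percutaneous and open thrombectomy as interventions, and Table 3A places both under interventions for flow dysfunction. Table 6J has no exclusion for thrombosis. An access found occluded and then declotted is therefore a true positive, although the target is stenosis.

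**Step 3: which way does this push the result?** Let a be the true positives in an open access, b the false positives, and T the treated thromboses entered through this row. The true-positive share moves from a/(a + b) to (a + T)/(a + b + T). With T and b above zero, the second is always larger. The direction follows from the table's rules.

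**Step 4: how far?** The SAP gives no value for a, b or T. With assumed counts a = 60 and b = 40:

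| T (assumed) | True-positive share |
|---|---|
| 0 | 60/100 = 60.0% |
| 5 | 65/105 = 61.9% |
| 10 | 70/110 = 63.6% |
| 20 | 80/120 = 66.7% |

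If a sensitivity is derived, with an assumed 20 false negatives, the base value is 60/80 = 75.0%. For T = 10 it becomes 70/90 = 77.8% if the thromboses count as true positives, or 60/90 = 66.7% if they count as misses. These figures show only how much the classification can matter; they are not estimates for this trial.

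**Step 5: is there a precedence rule elsewhere?** The only exclusion of thrombosis interventions found is the note to Table 2K. It concerns waiting times and does not reach Tables 2G, 3B, 6J, 8C or 8E.

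**The case against.** The strongest reply is that the indicators are defined by the protocol's decision rules, which are not shown. An absent thrill may properly trigger a notification, and deleting the row would make the totals disagree with what sites were sent. That is a good reason to keep a total that includes the row. It does not settle how the SAP classifies the event, because the SAP's own tables carry the row without any exclusion.

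It can also be said that the two columns of Table 6J concern different reports, one positive and one cleared, so a miss followed by a later finding is not strictly contradictory. That is correct. It is also true that the row is printed separately, so its contribution is visible. The pooled rows still absorb it.

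Several stronger readings are tempting, and the SAP does not support them:

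- *The safety comparison is compromised.* The thrombosis rate has its own definition, its own model in section 5.2.2 and its own row in Table 4A. The primary outcome counts interventions whatever their indication. Tables 2K, 3A and 7C also show thrombosis or thrombectomy separately.
- *The monitoring arm is favoured.* Table 6J has no arm columns, and section 2.7 has the access examined at every session without distinguishing arms.
- *Table 6D has the same fault.* It assesses flow measurements, and its three outcomes are separate cross-tables that need not be mutually exclusive. For the flow-dysfunction outcome, measurements taken with clinical signs present are already excluded.
- *The number of affected events can be obtained from planned follow-up.* The SAP gives no thrombosis rate. Such a product would also assume that every thrombosis generates a report carrying this item, while a table footnote says that reports were not transferred from two sites.

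**Conclusion.** The overlap is real and rests on the SAP's own text. As written, Table 6J lets a treated occlusion count as a correct prediction of stenosis, which biases its pooled rows upward. Tables 3B, 8C and 8E leave the indication for the same event undetermined. The amount is unknown, because it depends on how many thromboses are first recorded through this row.

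The reach is limited to descriptive and exploratory tables. Accuracy of clinical monitoring is not among the outcomes in section 5.1.2, item 6, where the accuracy outcome concerns flow measurements. The conclusion assumes that the unseen protocol does not already separate an occluded access from the other indicators; if it does, the SAP needs to carry that rule into its tables.

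**What to change.** Add one sentence to the SAP: for analysis, an access meeting the section 5.1.2 definition is classed as thrombosis. Then:

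- In Tables 3B, 8C and 8E, code the resulting intervention only under the thrombosis indication.
- In Table 6J, report the row for absent thrill and bruit separately. In the pooled rows, leave out reports that meet the thrombosis definition, from numerator and denominator alike, so that they are neither true nor false positives for stenosis. Show the total including them alongside, so that it still matches the notification rules.
- In Table 2G, a footnote pointing to the rule is enough.

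The cost is SAP wording and one recode of an item already collected. No new data are needed. The change concerns classification for analysis only and leaves the referral rules, the primary outcome and the thrombosis rate as they are.
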